See Electronic Signature Report _____ Date
[name] _____
Senior Principal Research Optometrist

Clinical Operations
Manager

See Electronic Signature Report _____ Date
[REDACTED]
[REDACTED]

Biostatistician

See Electronic Signature Report _____ Date
[REDACTED]
[REDACTED]

Data Management

See Electronic Signature Report _____ Date
[REDACTED]
[REDACTED]
[REDACTED]
[REDACTED]

Reviewer

See Electronic Signature Report _____ Date
[REDACTED]
[REDACTED]

Approver

See Electronic Signature Report _____ Date
[REDACTED]
[REDACTED]

CHANGE HISTORY

Version	Originator	Description of Change(s) and Section Number(s) Affected	Date
1.0	[name]	Original Protocol	10 August 2017
2.0	[name]	
Section 2.2 – updated Secondary Endpoint to “clinically significant (Grade 3 or 4) slit lamp findings.”
 
Section 6.4 – updated lens packaging information.
 
Section 14.2 – updated reference information and changed Table 1 to Table 4. Updated TOC.
 
Section 14.6 – Added section number for Secondary Analysis and updated to “Secondary endpoints will be summarized descriptively using all available data including data from unscheduled visits.”
 
Updated protocol version and date throughout.
	19 September 2017
3.0	[name]	
Figure 1 – updated study flowchart to clarify lens modification procedures
 
Section 7.2 – Updated Visit 1 instructions on Step 1.13 and 1.16 to clarify lens modification procedures.
 
Updated protocol version and date throughout
 
Section 5.2 - Removed the specific randomization letter codes
 
New medical monitor assigned to the study
 
Appendix C – Added package insert
	31 October 2017

SYNOPSIS

[figure not shown]
Protocol Title	Clinical Evaluation of etafilcon A with ketotifen
Sponsor	Johnson & Johnson Vision Care, Inc., [name]
Clinical Phase	Developmental phase: Phase 2
Trial Registration	This study will be registered on ClinicalTrials.gov by the Sponsor
Test Article(s)	Investigational Products: K-Lens: etafilcon A with 0.019 mg ketotifen Placebo: 1-Day ACUVUE® Brand Contact Lens
Wear and Replacement Schedules	Wear Schedule: Daily Disposable Replacement Schedule: Daily
Objectives	The purpose of this study is to evaluate the clinical performance of K-Lens produced on the new J&J Vision Care, Inc. manufacturing line in Limerick, Ireland.
Study Endpoints	
The primary endpoint is monocular contact lens best-corrected distance visual acuity on logMAR scale. This will be evaluated under high luminance and high contrast conditions at 4 meters from ETDRS charts at 1-Week Follow-up Visit.
 
The secondary endpoints are:
 
 • Proportion of eyes with significant (Grade 3 or 4) slit lamp findings • Proportion of eyes with unacceptable lens fitting 
Adverse events, subject reported ocular symptoms, subjective assessment of lens handling, number and reasons for discontinuation, number and reasons for unscheduled lens replacement including lens damage will be monitored and summarized.

Study Design	
This is a randomized, double-masked, bilateral, controlled, two-arm parallel group, multi-site, 1-Week dispensing study. Subjects are scheduled for 2 study visits:
 
 • Visit 1: Initial screening, baseline evaluation, lens assignment, lens dispensing and clinical assessments • Visit 2: Follow-up visit 6 to 9 days after the initial visit with clinical assessments and exit procedures. 
See the flowchart at the end of the synopsis for the schematic of the study visits and procedures of main observations.

Sample Size	This study will target to enroll approximately 132 subjects with a target completion of 80 subjects in the K-Lens arm and 40 in the Placebo arm.
Study Duration	The study duration will be approximately 8 weeks
Anticipated Study Population	The study populations will be healthy normal habitual contact lens wearers that are at least 18 years old and less than 40 years.
Eligibility Criteria	
Potential subjects must satisfy all of the following criteria to be enrolled in the study
 
 1. The subject must read, understand, and sign the STATEMENT OF INFORMED CONSENT and receive a fully executed copy of the form 2. Appear able and willing to adhere to the instructions set forth in this clinical protocol 3. Between 18 and 39 (inclusive) years of age at the time of baseline visit 4. The subject must be a habitual lens wearer for a least 6 days/week and for a minimum of 8 hours per day over the last month. 5. The subject's contact lens correction must be in the range of -1.00 D to -6.00 D (inclusive) in each eye. 6. The subject's refractive cylinder must be 1.00 D or less in each eye 7. Have a spherocylindrical best corrected visual acuity of 20/30 or better in each eye (Snellen Visual Acuity) 
Potential subjects who meet any of the following criteria will be excluded from participating in the study:
 
 1. Currently pregnant or lactating 2. Any systemic disease (e.g., Sjögren's Syndrome), allergies, infectious disease (e.g., hepatitis, tuberculosis), contagious immunosuppressive diseases (e.g., HIV), autoimmune disease (e.g. rheumatoid arthritis), or other diseases, by self-report, which are known to interfere with contact lens wear and/or participation in the study 3. Use of systemic medications (e.g., chronic steroid use) that are known to interfere with contact lens wear 4. Any ocular allergies, infections or other ocular abnormalities that are known to interfere with contact lens wear and/or participation in the study. This may include, but not be limited to entropion, ectropion, extrusions, chalazia, recurrent styes, glaucoma, history of recurrent corneal erosions, aphakia, or corneal distortion

	
 5. Any corneal distortion resulting from previous hard or rigid gas permeable contact lens wear, history of strabismus, or current monovision, multi-focal, or toric contact lens correction. 6. Any current use of rewetting drops or ocular medication 7. Any previous, or planned (during the course of the study) ocular surgery (e.g., radial keratotomy, PRK, LASIK, etc.) 8. Any grade 3 or greater slit lamp findings (e.g., edema, corneal neovascularization, corneal staining, tarsal abnormalities, conjunctival injection) on the FDA Biomicroscopy Scale 9. Any previous history or signs of a contact lens-related corneal inflammatory event (e.g., past peripheral ulcer or round peripheral scar), or any other ocular abnormality that would contraindicate contact lens wear 10. Any known hypersensitivity or allergic reaction to ketotifen 11. Participation in any eye drop, contact lens or lens care product clinical trial within 14 days prior to study enrollment 12. Employee or immediate family member of an employee of clinical site (e.g., Investigator, Coordinator, Technician)
Disallowed Medications/Interventions	No ocular medications (Rx or OTC) or any systemic medications that (e.g., chronic steroid use) are known to interfere with contact lens wear
Measurements and Procedures	Monocular contact lens best-corrected distance visual acuity (measured via logMAR visual acuity charts)
Microbiology or Other Laboratory Testing	None
Study Termination	The occurrence of one or more Unanticipated Adverse Device Effect (UADE), or any SAE where relationship to study agent cannot be ruled out, will result in stopping further dispensing investigational product. In the event of a UADE or SAE, the Sponsor Medical Monitor may unmask the treatment regimen of subject(s) and may discuss this with the Principal Investigator before any further subjects are enrolled.
Ancillary Supplies/ Study-Specific Materials	None

Principal Investigator(s) and Study Institution(s)/Site(s)	A full list of Principal Investigators, clinical sites, and institutions is kept separately from the Study Protocol and is included in the study Trial Master File.
--	---

Figure 1: Study Flowchart

COMMONLY USED ABBREVIATIONS AND DEFINITIONS OF TERMS

ADE	Adverse Device Effect
AE	Adverse Event/Adverse Experience
BCVA	Best Corrected Visual Acuity
BSCVA	Best Spectacle Corrected Visual Acuity
CFR	Code of Federal Regulations
CLUE	Contact Lens User Experience
CRA	Clinical Research Associate
CRF	Case Report Form
CRO	Contract Research Organization
CT	Center Thickness
■■■■■	■■■■■
D	Diopter
DMC	Data Monitoring Committee
eCRF	Electronic Case Report Form
EDC	Electronic Data Capture
ETDRS	Early Treatment Diabetic Retinopathy Study
FDA	Food and Drug Administration
GCP	Good Clinical Practice
HIPAA	Health Insurance Portability and Accountability Act
IB	Investigator's Brochure
ICF	Informed Consent Form
ICH	International Conference on Harmonization
IDE	Investigational Device Exemption
IEC	Independent Ethics Committee
IRB	Institutional Review Board
ISO	International Organization for Standardization
ITT	Intent-to-Treat
JJVC	Johnson & Johnson Vision Care, Inc.
logMAR	Logarithm of Minimal Angle of Resolution
MOP	Manual of Procedures
NIH	National Institutes of Health
OD	Right Eye
OS	Left Eye
OTC	Over the Counter
OU	Both Eyes
PD	Protocol Deviation
PI	Principal Investigator
PIG	Patient Instruction Guide
PQC	Product Quality Complaint
PRO	Patient Reported Outcome
QA	Quality Assurance
QC	Quality Control
Rx	Prescription
SAE	Serious Adverse Event/Serious Adverse Experience
SAP	Statistical Analysis Plan

SAS	Statistical Analysis System
SD	Standard Deviation
SOP	Standard Operating Procedure
UADE	Unanticipated Adverse Device Effect
USADE	Unanticipated Serious Adverse Device Effect
VA	Visual Acuity

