11. STUDY TERMINATION

The occurrence of one or more Unanticipated Serious Adverse Device Effect (USADE), or any SAE where the relationship to study agent cannot be ruled out, may result in stopping further dispensing of test article. In the event of a USADE or SAE, the Sponsor may unmask the treatment regimen for the subject(s) and will discuss this with the Investigator before any further subjects are enrolled.

The Sponsor will determine when a study will be stopped. The Principal Investigator always has the discretion to initiate stopping the study based on patient safety or if information indicates the study's results are compromised.

JJVC reserves the right to terminate the study at any time for any reason. Additionally, the IEC/IRB reserves the right to terminate the study if an unreasonable risk is determined. The study can be terminated by the Principal Investigator at the individual clinical site due to specific clinical observations, if in their opinion, after a discussion with JJVC, it is determined that it would be unwise to continue at the clinical site.

JJVC (and the IEC/IRB and DMC, if applicable) will evaluate all adverse events. If it is determined that an adverse event presents an unreasonable risk, the investigation, or that part of the investigation presenting the risk, will be terminated, as soon as possible.

Should the study be terminated (either prematurely or as scheduled), the Investigator will notify the IEC/IRB and Regulatory Authority as required by local regulatory requirements.

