13.4.1 Reporting Adverse Events to Sponsor

Serious/Significant Adverse Events

The Investigator will inform the sponsor of all serious/significant adverse events occurring during the study period as soon as possible by e-mail, fax, or telephone, but no later than 24 hours following discovery of the event. The Investigator is obligated to pursue and obtain information requested by the Sponsor in addition to that information reported on the eCRF. All subjects experiencing a serious/significant adverse event must be followed up and all outcomes must be reported.

When medically necessary, the Investigator may break the randomization code to determine the identity of the treatment that the subject received. The Sponsor and study monitor should be notified prior to unmasking the test articles.

In the event of a serious/significant adverse event, the Investigator must:

- Notify the Sponsor immediately
- Obtain and maintain in the subject's records all pertinent medical information and medical judgment for colleagues who assisted in the treatment and follow-up of the subject
- Provide the Sponsor with a complete case history which includes a statement as to whether the event was or was not related to the use of the test article
- Notify the IEC/IRB as required by the IEC/IRB reporting procedure according to national regulations

Unanticipated (Serious) Adverse Device Effect (UADE)

In the event of an Unanticipated (Serious) Adverse Device Effect (UADE), the Investigator will submit a report of the UADE to the Sponsor and IEC/IRB as soon as possible, but no later than 24 hours after the Investigator first learns of the effect. This report is in addition to the immediate notification mentioned above.

The Sponsor must conduct an evaluation of the UADE and must report the results of the evaluation to FDA, the IEC/IRB and participating Investigators within 10 working days after the Sponsor first receives notification of the effect.

Non-Serious Adverse Events

All non-serious adverse events, including non-serious adverse device effects, will be reported to the sponsor by the Investigator no later than 2 days from discovery.

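### After a serious adverse event that may be related, the synopsis requires a halt in dispensing and Section 11 only permits one; the duty to discuss with the investigator differs the other way round

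*Protocol*

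**What the plan says.** The rule appears twice in the current protocol (v3.0).

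**Synopsis, Study Termination.** There are two triggers. One is any unanticipated adverse device effect, abbreviated UADE. The other, with its consequence, reads: "or any SAE where relationship to study agent cannot be ruled out, will result in stopping further dispensing investigational product". A separate sentence deals with unmasking after either kind of event: "the Sponsor Medical Monitor may unmask the treatment regimen of subject(s) and may discuss this with the Principal Investigator before any further subjects are enrolled".

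**Section 11, Study Termination.** The first trigger carries a different label: "The occurrence of one or more Unanticipated Serious Adverse Device Effect (USADE". The second is the same SAE trigger, but its consequence is conditional: "or any SAE where the relationship to study agent cannot be ruled out, may result in stopping further dispensing of test article". The matching sentence on unmasking reads: "the Sponsor may unmask the treatment regimen for the subject(s) and will discuss this with the Investigator before any further subjects are enrolled".

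Section 11 adds general powers. On who decides, it says: "The Sponsor will determine when a study will be stopped". A further clause applies once adverse events have been evaluated and a judgement reached: "that an adverse event presents an unreasonable risk, the investigation, or that part of the investigation presenting the risk, will be terminated".

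**The concern.** A halting rule should tell the sponsor and the sites what happens once a stated event has occurred. Here the same event, an SAE whose relationship to the study agent cannot be excluded, leads to a compulsory halt in one place and an optional halt in the other. The discussion that precedes further enrolment is optional in the first and compulsory in the second.

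This is the only study-level rule that ties a specified event to a halt in further dispensing. The other powers in Section 11 depend on a judgement reached after evaluation. One event is enough to invoke the rule, and there is little time to settle its meaning during conduct: Section 4 plans six sites and about 8 weeks, Section 14.8 plans no interim analysis, and Section 11 mentions a data monitoring committee only where applicable.

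**Working it through.** The plan states no figure to reproduce on this point, so the check is mainly a comparison of the two texts.

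**1. Side by side**

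| Element | Synopsis | Section 11 |
|---|---|---|
| Device-effect trigger | UADE | USADE |
| SAE trigger | relationship to study agent cannot be ruled out | the same |
| Further dispensing | *will* stop | *may* stop |
| Who may unmask | Sponsor Medical Monitor | Sponsor |
| Discussion before further enrolment | *may* | *will* |
| Discussion with | Principal Investigator | Investigator |

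**2. Is the trigger really the same?** For the SAE, yes: the wording is almost identical. For the device effect, the labels differ but no difference in events is shown. Section 13.1 already limits a UADE to serious effects, life-threatening problems, death or other serious problems. Section 13.4.1 places the word serious inside the UADE term: "In the event of an Unanticipated (Serious) Adverse Device Effect (UADE), the Investigator will submit a report". USADE is expanded in the abbreviation list but not defined in Section 13.1. This is an inconsistency of wording only.

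**3. What each text allows after one qualifying SAE**

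| Sponsor's course | Synopsis | Section 11 |
|---|---|---|
| Halt, and discuss before further enrolment | complies | complies |
| Halt, then enrol again without discussion | complies | breaches |
| Keep dispensing, and discuss before further enrolment | breaches | complies |
| Keep dispensing, and enrol without discussion | breaches | breaches |

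Two of the four courses are acceptable under one text and a breach of the other.

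**4. Does anything rank the two texts?** No. The only precedence clause is in SAP section 1, and it lets the SAP override protocol Section 14 alone. The protocol's change history lists no edit to Section 11 or to the synopsis termination row, and both sentences are complete and unredacted.

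**5. How likely is the rule to be needed?** The documents give no SAE rate, so this is an illustration under assumed rates. With *p* the per-subject probability of a qualifying SAE, subjects independent, and 132 randomized (Section 4.1, Table 1):

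P(at least one) = 1 − (1 − *p*)^132

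| Assumed *p* | Calculation | P(at least one) |
|---|---|---|
| 0.01% | 1 − 0.9999^132 | 1.3% |
| 0.1% | 1 − 0.999^132 | 12.4% |
| 0.5% | 1 − 0.995^132 | 48.4% |
| 1% | 1 − 0.99^132 | 73.5% |

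Neither text says whether a halt would be temporary or permanent, so no loss of sample size can be estimated.

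**The case against.** The best reply is that the two texts can be followed together. An optional halt permits what a compulsory halt requires, and the same holds for the discussion; a sponsor that halts and discusses satisfies both. That is true, as the first row of the second table shows. It does not settle whether either step is required, which is what a halting rule has to say.

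Other objections narrow the point without removing it:

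- **The actor.** The Sponsor Medical Monitor is a sponsor role, and Section 5.2 gives that role access to the decode information. The synopsis may simply name the person who acts for the sponsor. The difference in actor is therefore minor beside the two differences in obligation.
- **The discussion trigger.** In both texts the unmask-and-discuss sentence refers to any SAE, with no condition on relationship, so it is broader than the stopping trigger. A qualifying SAE still falls within it, and the conflict arises for that event.
- **Other event-based rules.** Section 8.2 withdraws individual subjects, for example after a corneal infiltrative event, and Section 7.2 discontinues a subject for unacceptable fit. These rules concern one subject and do not halt dispensing to others.
- **The probabilities.** They rest wholly on assumed rates. In healthy habitual wearers using lenses for 6 to 9 days the true rate may lie at or below the bottom of the range. The inconsistency does not depend on them.
- **Termination for unreasonable risk.** This protection applies under either reading, but only after a judgement has been made.

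**Conclusion.** The concern holds. For one and the same SAE, the synopsis makes the halt compulsory and the discussion optional, while Section 11 makes the halt optional and the discussion compulsory, and no clause says which governs. The conclusion rests on the current wording alone and needs no assumption about event rates.

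This is a problem of safety conduct. It leaves the sample size, type I error and primary analysis unchanged. It should be corrected, because a single event would leave the sponsor's obligations undefined. The UADE/USADE difference is a secondary matter of terminology.

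**What to change.** Reconcile the synopsis and Section 11 so that both state:

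- one trigger, using a term defined in Section 13.1;
- one consequence for dispensing, marked clearly as mandatory or discretionary;
- one responsible party, and one obligation, for the discussion with the investigator before further enrolment, with its own trigger stated.

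The choice of rule belongs to the sponsor, and no view is taken on it here. The cost is a wording amendment to the synopsis, Section 11 or both, with no extra data, subjects or procedures.

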1. INTRODUCTION AND BACKGROUND

The etafilcon A with ketotifen contact lens is being developed as a novel drug/device combination product that incorporates the anti-allergy agent ketotifen with the same material as the 1•DAY ACUVUE® Brand disposable contact lens (etafilcon A daily disposable contact lens). This new product will be referred to hereafter as K-Lens. The control 1•DAY ACUVUE® Brand disposable contact lens will be referred to hereafter as Placebo. Ocular allergy, and the discomfort associated with its signs and symptoms, is a common cause of contact lens intolerance and of seasonal exacerbation of eye allergy symptoms in contact lens wearers.^{5,6} The creation of a concomitant system of an anti-allergy agent and a contact lens will offer significant advantages over existing therapies in that it allows contact lens users to continue wearing their lenses during the allergy season while preventing ocular itching associated with allergic conjunctivitis.

Ketotifen fumarate, a benzocycloheptathiophene derivative, is an approved noncompetitive H₁ receptor antagonist that stabilizes mast cells and prevents eosinophil accumulation, thus providing multiaction therapy. Ketotifen fumarate ophthalmic solution is an effective, safe, and well-tolerated therapy for the management of ocular allergy with a duration of action of up to 12 hours as demonstrated in the conjunctival allergen challenge mode.^{7,8}

K-Lens has been evaluated for safety, tolerability, and efficacy (prevention of ocular itching) in previous studies.⁹⁻²⁰ The results of these studies have shown it to be safe, tolerable and efficacious. Two (2) pivotal Phase 3 studies have shown that K-Lens was effective in the prevention of ocular itching associated with allergic conjunctivitis at 15 minutes and 12 hours following lens insertion.^{16,17} The goal of this study is to evaluate the clinical performance of K-Lens produced on the new J&J Vision Care, Inc. manufacturing line in Limerick, Ireland, in a population of normal, healthy, habitual contact lens wearers.

1.1. Name and Descriptions of Investigational Products

The K-Lens is a combination product consisting of an etafilcon A soft hydrophilic contact lens with 0.019 mg ketotifen. Additional information pertaining to the device and drug components is listed below:

Device component – The device component is an etafilcon A soft contact lens equivalent to 1-DAY ACUVUE® Brand Contact Lenses. This product is currently cleared by Food & Drug Administration (FDA) under 510(k) K013973. The predicate device in this 510(k) was ACUVUE® (etafilcon A) Brand Contact Lenses, approved by FDA under PMA N18-033.

The etafilcon A soft hydrophilic contact lenses have an extensive history on the United States (US) market and are indicated for the correction of refractive ametropia (myopia and hyperopia) in phakic or aphakic persons with non-diseased eyes who may have 1.00 D or less of astigmatism. Lenses are to be worn as a daily wear contact lens (periods of less than 24 hours while awake) and disposed of after removal.

Drug component – The drug component, ketotifen, is the active ingredient in the currently marketed eye drop, ZADITOR® (ketotifen fumarate ophthalmic solution, 0.035%)

manufactured by Alcon Pharmaceuticals. ZADITOR® was originally approved under NDA 21-0166 in 1999 as a prescription drug for the prevention of ocular itching associated with allergic conjunctivitis (selective H₁ antihistamine/mast cell stabilizer) and switched to over-the-counter in 2006 (NDA 21-066/S011). The drug component may use the Reference Listed Drug under NDA 021066 (ZADITOR® [ketotifen fumarate ophthalmic solution, 0.035%]).

